Confidential

More specifically, for patients in treatment arms 1 and 2 that switch to 10 mg/kg after 3 doses, the measurement right before patients received the first dose of MCS110 10 mg/kg (4th dose from screening) will be treated as the new baseline and assessment time-points will be adjusted accordingly. This may apply to all analyses in Section 9 if necessary.

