7.1 Data post-surgery will not be used for primary analysis - Primary Endpoint

Part A, B and C pooled for weeks 1 to 4 (referred as 'Part A*' hereafter)

The tumor size (volume) as assessed by MRI technique up to and including week 4 will be the primary measure of efficacy. This data will be listed as collected.

Consolidated tumor volume will be calculated as the geometric mean from two readers. Summary statistics of the consolidated tumor volume will be presented by treatment and visit time. The tumor volume measured at screening is treated as baseline. The percent change and absolute change from baseline of the consolidated tumor volume will be summarized in the same fashion. Waterfall plot on percent change from baseline after 4 weeks will be produced. The tumor size at baseline and after 4 weeks will be log transformed. The log ratio to baseline of the tumor size (change from baseline of log transformed volume) will be the primary measure of efficacy for the single dosing part of the study (Part A*).

The analysis of the primary endpoint will quantify the accumulation of evidence about the treatment effect as patients complete their 4 week treatment. The evidence will be summarized in the posterior distributions of the treatment group means and their differences. These posterior distributions will be updated after certain patients complete the 4 week treatment.

For the analysis, the distributional model for the observed data (log ratio) will be the normal model with unknown parameters μ and σ , with μ being the parameter of primary interest (treatment mean) and σ representing the sampling error. This model will be applied to each MCS110 dose group separately. Little prior information is available for these parameters and therefore non-informative prior distributions will be placed on them. For μ a normal prior distribution centered at 0 (no treatment effect) will be used with large standard deviation, and for σ a uniform (0,2) prior distribution.

The model is formally described below, LR being the log ratio of tumor volume:

Likelihood

$$LR_i \sim N(\mu, \sigma)$$

with

$$\mu = \mu_p \text{ for observations from placebo group}$$

$$\mu = \mu_m \text{ for observations from MCS110 group}$$

Prior distributions on treatment means μ 's

$$\mu_p \sim N(0, 0.3)$$

$$\mu_m \sim N(0, 10) \text{ * i.e. Neutral prior or}$$

$$\mu_m \sim N(0, 0.3) \text{ * i.e. Skeptical prior}$$

Prior distributions on sigma

$$\sigma \sim \text{Uniform}(0,2)$$

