The same model as above will also be applied to compare the efficacy of the 3 mg/kg and 5 mg/kg to the 10 mg/kg dose (instead of Placebo).

Part B and C (referenced as Part B* hereafter)

Part B includes all data from multiple dosing Parts. In Part B, treatment group 1 = MCS110 throughout the trial, treatment group 2 = Placebo for the first dose and MCS110 from the second dose. In Part C, treatment arm 1 = MCS110 3 mg/kg, treatment arm 2 = MCS110 5 mg/kg, treatment arm 3 = MCS110 10 mg/kg, for patients in treatment arms 1 and 2 that switch to 10 mg/kg after 3 doses, they will be included in their original treatment group for the first 3 doses and will added in a separate group after that (4= MCS110 3 mg/kg for 3 doses and 10 mg/kg afterwards and 5= MCS110 5 mg/kg for 3 doses and 10 mg/kg afterwards), no re-calculation of baseline will occur for the people who change treatments.

Tumor volumes will be listed at each MRI assessment timepoint till the end of the study by treatment groups.

Part B*: MCS110 data only, by including data starting from the 1st dose of MCS110 in all treatment groups of Parts B and C. More specifically, for Part B treatment group 2, the measurement right before patients receiving the first dose of MCS110 (2nd dose from screening) will be treated as the new baseline and assessment time-points will be adjusted accordingly. Summary statistics of the consolidated tumor volume for the raw values, percent change and absolute change from baseline.

Arithmetic mean (+/-) SE on percent change from baseline vs time plot will be produced for Part B*. Waterfall plot of the maximum reduction until 8 Weeks after last dose will be produced in regards of number of doses received.

Overall Time to complete tumor ablation will be summarised up to the primary endpoint (8 weeks after the last MCS110 dose), along with a summary of overall time to $\geq 50\%$, and $\geq 80\%$ ablation. The number and frequency of patients reaching each level will also be included in the summary.

Overall Time to complete ablation is the time (in weeks) - from first MCS110 dose to the first time when there is no tumor detected. Overall time to $\geq 50\%$, and $\geq 80\%$ ablation is the time from first MCS110 dose to reach maximum ablation of [50%, 80%) and [80%, complete) respectively.

Part C

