Tumor volumes will be listed and descriptively summarized at each MRI assessment time by treatment arm (treatment arm 1 = MCS110 3 mg/kg, treatment arm 2 = MCS110 5 mg/kg, treatment arm 3 = MCS110 10 mg/kg). For patients in treatment arms 1 and 2 that switch to 10 mg/kg after 3 doses, they will be treated as a separate group throughout the study (4= MCS110 3 mg/kg for 3 doses and 10 mg/kg afterwards and 5= MCS110 5 mg/kg for 3 doses and 10 mg/kg afterwards) This approach will be applied for all analyses of Part C where the treatment group is used. In addition, incidences of patients with partial response (PR), stable disease (SD) and progressive disease (PD) will be listed by treatment arm.

All summary tables (tumor volumes and response) will also be provided by age group (<18 years and ≥ 18 years).

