7.1.2 Supportive analyses

Part A, Part B and Part C pooled for weeks 1 to 4 (Part A*)

As a supportive analysis, log ratio to baseline of tumor volume at week 4 may be subjected to an Analysis of Covariance (ANCOVA) model. The model will include log transformed tumor volume at baseline and a factor for treatment. Point estimates and 95% confidence interval will be calculated for MCS110 and Placebo separately, and for the difference of means between MCS110 and Placebo. Results will then be transformed back to the original scale.

Part B*:

To study the time course of tumor volume reduction from baseline, a repeated measures ANCOVA model on log ratio to baseline will be fit by resetting the tumor volume at week 4 as baseline for patients in treatment group 2 and the visit number will be adjusted accordingly. The model will include log tumor volume at baseline and visit as fixed effects. Standard fit statistics will be used to determine the best variance-covariance structure. Point estimates and 95% confidence interval will be calculated at each visit. Baseline adjusted tumor volume (+/- SE) over time will be plotted.

Part C:

As a supportive analysis, log ratio to baseline of tumor volume at week 4 may be subjected to an Analysis of Covariance (ANCOVA) model. The model will include log transformed tumor volume at baseline and a factor for treatment. Point estimates and 95% confidence interval will be calculated for each treatment arm and for the difference of means between treatment groups. Results will then be transformed back to the original scale.

The statistical analysis will also be provided by age group (<18 years and ≥18 years).

Parts A, B and C :

A dose-time-response model (Lange and Schmidli 2015) will be used to analyze tumor response data (log ratio to baseline of tumor volume) from Parts A, B, and C. The following equation will be used for the latent concentration $C(t)$ of a patient who receives K doses with dose D_k received at time t_k , $k=1, \dots, K$:

$$C(t) = \sum_{k=1}^q \frac{D_k \theta_1}{\theta_1 - \theta_2} \left\{ \exp \left[-\theta_2 \left(t - \sum_{j=0}^{k-1} \delta_j \right) \right] - \exp \left[-\theta_1 \left(t - \sum_{j=0}^{k-1} \delta_j \right) \right] \right\}$$

where $\delta_0=t_1$, $\delta_j=t_{j+1} - t_j$ for $j=1, \dots, K-1$ and $q \in \{1, \dots, K - 1\}$ is such that $t_q < t \leq t_{q+1}$ and $q=K$ if $t > t_K$.

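### The SAP's Part C grouping removes 3 and 5 mg/kg patients who respond poorly at week 12 from their arm back to baseline, so arm summaries up to week 12 favour the lower doses

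*SAP*

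**What the plan says.** **Part C grouping.** SAP section 7.1, Part C, summarises tumor volume by arm at every MRI visit. Of patients in arms 1 (3 mg/kg) and 2 (5 mg/kg) who move to 10 mg/kg after three doses, it says "they will be treated as a separate group throughout the study", as groups 4 and 5. It adds: "This approach will be applied for all analyses of Part C where the treatment group is used".

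**Part B\* grouping.** The same SAP section, under Part B and C, defines the same arms and the same groups 4 and 5. There, however, "they will be included in their original treatment group for the first 3 doses and will added in a separate group after that".

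**What triggers the switch.** Protocol sections 3.2.2 and 5.5.5.2 and SAP section 2.4 send a 3 or 5 mg/kg patient who tolerates the drug to 10 mg/kg when the week-12 MRI shows a reduction below 45%. That MRI precedes dose 4. In the 10 mg/kg arm, a reduction below 45% changes only the number of further doses (protocol section 5.5.5.2), and the patient stays in arm 3.

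**Comparative analyses.** The optional Part C ANCOVA at week 4 (SAP section 7.1.2) states: "Point estimates and 95% confidence interval will be calculated for each treatment arm and for the difference of means between treatment groups". The Bayesian week-4 model is also "applied to compare the efficacy of the 3 mg/kg and 5 mg/kg to the 10 mg/kg dose". Its description says "This model will be applied to each MCS110 dose group separately" but does not say whether a switcher counts under the assigned dose.

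**Baseline of switchers.** Protocol section 9.4.2 says "the measurement right before patients received the first dose of MCS110 10 mg/kg (4th dose from screening) will be treated as the new baseline". SAP section 7.1 says "no re-calculation of baseline will occur for the people who change treatments".

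**The concern.** Through the pre-dose week-12 assessments, every Part C patient has received only the assigned dose. This is the window in which the three doses can be compared as randomised. Under the Part C rule, membership of arms 1 and 2 at weeks 4, 8 and 12 depends on the week-12 result. Any patient who tolerates the drug, reaches the week-12 decision and remains in a low-dose arm shows at least a 45% reduction there by construction. That is also the threshold that protocol section 3.2.2 uses to define efficacy equal to 10 mg/kg. The 10 mg/kg arm keeps its poor responders.

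Part C exists to learn whether a lower dose does as well as 10 mg/kg (protocol sections 1.4 and 3.2.3.2). The printed arm means, and the week-4 arm differences if the ANCOVA uses these groups, would lean towards yes whatever the truth. A programmer also has two different rules for the same patients over the same visits.

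**Working it through.** **The plan's own figure.** Protocol section 9.13 claims more than 80% power with 6 patients per lower-dose arm. It gives no SD, effect or decision rule. Over plausible inputs (6 vs 3 or 6 vs 19 patients, SD 0.28–0.60, low-dose reduction 0–30% against 50%), power runs from 12% to nearly 100%. The claim can be neither confirmed nor refuted, and nothing below depends on it.

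**Inputs**
- Arm sizes 6 and 3: protocol section 5.2.3.
- 10 mg/kg: 50% reduction after three doses (protocol section 1.4) and 40% at week 4 (single-dose average, protocol synopsis).
- SD of the log ratio: 0.2·√2 = 0.283 and 0.3·√2 = 0.424, the Part A scenarios in protocol section 9.13. No Part C SD is visible, so this is an assumption.
- True low-dose reductions of 30% or 50% at week 12 and 20% at week 4: assumptions.
- All patients tolerate the drug and have a week-12 MRI.

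**Week 12, formulas.** A patient stays in the arm if the log ratio is at most log 0.55. With true reduction r:
- a = (log 0.55 − log(1 − r))/SD and P(stay) = p = Φ(a)
- mean log ratio of those retained = log(1 − r) − SD·φ(a)/p
- P(arm empty) = (1 − p)^6

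For r = 30%, SD 0.283: a = (−0.598 + 0.357)/0.283 = −0.853 and p = 0.197. The retained mean is −0.357 − 0.283 × 1.408 = −0.755, a reduction of 1 − exp(−0.755) = 53%.

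As randomised, the chance that the low-dose mean log ratio is at or below the 10 mg/kg mean is Φ((log 0.5 − log(1 − r))/(SD·√(1/6 + 1/3))). For r = 30% this is Φ(−1.68) = 0.046 and Φ(−1.12) = 0.131. The chance under the Part C rule comes from simulation.

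| Week 12 (SD 0.283 / 0.424) | True 30% | True 50% |
|---|---|---|
| Retained of 6 | 1.2 / 1.7 | 3.8 / 3.5 |
| Reduction shown | 53% / 58% | 58% / 62% |
| Arm empty | 27% / 13% | 0.2% / 0.5% |
| At least as good as 10 mg/kg, all trials | 45% / 61% | 81% / 83% |
| Same, as randomised | 5% / 13% | 50% / 50% |

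Among trials with a non-empty arm, the 30% case gives 61% / 71%.

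**Week 4.** If variation is measurement error only, as in protocol section 9.13, the week-4 and week-12 log ratios share just the baseline error, so their correlation is 0.5. For a true 30% at week 12, the volume ratio of retained patients at week 4 is multiplied by exp(−0.5 × 0.283 × 1.408) = 0.819, or exp(−0.5 × 0.424 × 1.192) = 0.777. A true 20% then shows as 1 − 0.8 × 0.819 = 34%, or 1 − 0.8 × 0.777 = 38%. Against 40% on 10 mg/kg, the low dose looks at least as good in 27% / 40% of all trials (37% / 46% of non-empty ones), against 8% / 17% as randomised, before baseline adjustment.

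**After week 12.** Selection persists among non-switchers. Under the same model, a true 30% eight weeks after the last dose shows as 1 − 0.7 × 0.819 = 43%, or 1 − 0.7 × 0.777 = 46%. Both grouping rules share this, so it calls for labelling.

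**The case against.** The strongest reply concerns weight. The dose-time-response model works from doses received and is unaffected. The Part B\* displays for doses 1–3 keep switchers in their arm. The Bayesian comparison of 3 and 5 mg/kg with 10 mg/kg is probably unaffected, since it reuses a week-4 model by dose group. What remains is descriptive tables and an ANCOVA that may not be run. The primary time point, eight weeks after the last dose, falls after the switch, where both rules use groups 4 and 5. Individual dose decisions at week 12 do not rest on these tables. Groups 4 and 5 are shown, so a reader could rebuild the arm mean, and an arm of one or two patients would be visibly a remnant. All of this stands, and it limits the severity.

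The two texts might also be read as separate displays, one with time-varying groups and one by complete regimen. That does not settle the matter: both define the Part C arms, and the Part C text claims every Part C analysis by treatment group. If the difference is deliberate, the Part C version still selects on outcome.

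The percentages are illustrative. The low-dose effects are assumed, the SDs are Part A planning values, and the comparison orders mean log ratios, which is not an SAP criterion. There is no bias if nobody switches, and a patient below 45% who does not tolerate the drug falls outside the switch rule. None of this changes the direction.

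**Conclusion.** The concern holds. As written, the Part C grouping conditions low-dose arm membership up to week 12 on the week-12 outcome and leaves the 10 mg/kg arm whole. Whenever patients switch for insufficient response, the printed low-dose means are biased in favour of the lower doses. This follows from the rule itself and needs no assumption about effect or SD.

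The size does depend on the assumptions listed. On those, a clearly inferior low dose would look at least as good as 10 mg/kg in about half of trials at week 12, and an equally effective one would look at least as good in about four of five. Because the outputs are mainly descriptive and the switcher groups remain visible, this should be fixed but does not undermine the trial. The disagreement between protocol and SAP on the switchers' baseline is separate: it affects data after the switch and does not cause this bias.

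**What to change.** 1. **SAP section 7.1, Part C.** Replace the whole-study rule with: *Patients in arms 1 and 2 who switch stay in their initially assigned arm for all Part C data up to and including the pre-dose week-12 assessments, and are shown as groups 4 and 5 only from dose 4 onward.* This is the rule the Part B\* text already uses.
2. **SAP section 7.1.2, Part C ANCOVA.** State that the treatment factor is the initially assigned dose.
3. **SAP section 7.1, Bayesian dose comparison.** Add one line that patients are grouped by initially assigned dose.
4. **After week 12, including eight weeks after the last dose.** Label non-switcher summaries as selected on week-12 response. If a display by initial arm is added, flag the switchers and state that it includes the effect of later 10 mg/kg doses, so it does not estimate the lower dose alone.
5. **Baseline of switchers.** Reconcile protocol section 9.4.2 with SAP section 7.1.

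The cost is SAP wording, a changed group derivation and one reconciliation with the protocol. No new data are needed. The lower-dose figures may look less favourable.

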3.2.2 Study design Part C

The study CMCS110X2201 Part C is a randomized, double-blind, parallel-arm adaptive dose exploration study part. Approximately 15 patients, including adults and adolescents (>12 years old), will be randomized to receive 3 mg/kg, 5 mg/kg or 10 mg/kg MCS110 in a ratio of approximately 2:2:1 and a potential further extension of the efficient lower dose arm. Tumor volume reduction after 3 doses, assessed by MRI at week 12, will guide the decision on whether to continue with the initial dosing (3 mg/kg or 5mg/kg) or increase for the following three doses to 10 mg/kg to allow the patient to benefit from the drug.

The adult patients will follow Assessment schedule Part C.

The adolescent patients will follow Assessment Schedule Part C-Adolescent patients, adapted to reduce the required blood volume to maximum 25 mL per time point and 50 mL in 8 weeks (Howie 2011).

Conditions of dose level change after 3 doses

Patients enrolled in 3 mg/kg and 5 mg/kg arms: 3 additional MCS110 doses of the same dose will be administered, if MCS110 is well tolerated and if a reduction in tumor volume of >45%can be demonstrated after the 3rd MCS110 dose evaluated by MRI taken just before the 4th dose. This MRI is reflecting potential efficacy of 3 doses. If the drug is well tolerated and the tumor volume reduction is <45%, then three additional MCS110 doses of 10 mg/kg will be administered.

Process of dosing after 3 doses

All patients within each arm will receive 3 doses of the same initial dose at Day 1, week 4 and week 8.

At week 12, an MRI and safety examinations will be taken before the planned 4th dose. The unblinded statistician(s) and an unblinded Novartis medical person (unblinded safety reviewer) will review the tumor volume reduction data from baseline to week 12 MRI and patient's safety data. The unblinded safety reviewer will inform the site's unblinded pharmacist on the dose level to administer at week 12:

- Patients enrolled in 3 mg/kg and 5 mg/kg arms can receive same initial dose or increase to 10 mg/kg.
- Patients enrolled in 10 mg/kg arm: can either stop after 4 doses or receive up to 6 doses of 10 mg/kg under conditions described in the Section 5.5.5.2 (Dosing extension to 6) consecutive doses once every 4 weeks).

Corporate Confidential Information

The primary outcome of Part C of the study will be the tumor volume after multiple doses of MCS110 determined by MRI which will be assessed 8 weeks after the last dose of MCS110.

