5.4 Treatment blinding

Part A and first dose Part B

This is a double blind study: patients, investigator staff (except the unblinded pharmacist), persons performing the assessments, and data analysts will remain blind to the identity of study treatments according to the specifications provided in Appendix 2.

A safety review will be carried out after each patient completes the 4-week treatment period, therefore the independent safety reviewer will be unblinded on an ongoing basis.

Randomization data are kept strictly confidential until the time of unblinding for the respective person(s). Further information regarding blinding and unblinding is presented in Appendix 2. The identity of the treatments will be concealed by the use of study drugs that are all identical in packaging, labeling, schedule of administration and appearance. Unblinding will only occur in the case of patient emergencies (see Section 5.5.10), at the time of the interim analysis and at the conclusion of the study.

Part B

Double-blind study part will be followed by an open label part from the second to the sixth dose.

Day 1 treatment will be maintained double blinded until week 12. At week 12, Day 1 treatment will be un-blinded in order to allow Day 1 placebo patients to receive two more MCS110 doses in open label.

Part C

28 weeks double-blind treatment period study part will be followed by an open label part.

Day 1 treatment will be maintained double-blinded until primary endpoint reached at Week 28 (or until any premature primary endpoint) to the Novartis clinical team and the investigator.

Following week 12 MRI, Novartis independent statistician (independent from the clinical study team) will proceed to the un-blinding and will share allocated dose level with an unblinded Novartis medical person (independent from the clinical team) who will review patient's safety profile and tumor volume reduction. The unblinded medical person will determine if the patient fulfills dose change conditions. The site's unblinded pharmacist will be informed by an independent study team member of potential dose change.

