If a patient develops periorbitalswelling, subsequent dosing (e.g., 4 wks, 8 wks) will be put on hold until one week after the swelling has resolved.

If a patient develops any adverse event considered as drug related by the investigator, which has not resolved before the following dose, next dosing will be delayed until considered resolved.

If there are abnormal hematology and / or biochemistry laboratory values (CTCAE grade 3) judged as clinically significant by the Investigator, the next dose will be delayed until abnormalities have resolved. Isolated CK increase with normal troponin T and aldolase is not considered a safety concern even if reaching CTCAE grade 3.

Part B: If dosing of 4 times 10 mg/kg MCS110 (once every 4 weeks) is exceeding the initial 13 weeks dosing period, (due to occurrence of AEs) further dosing will be allowed up to week 20 if all AEs had resolved for more than a week and efficacy assessment demonstrates response to treatment (>50 % of tumor volume reduction after 3^{rd} dose in Part B, 45% in Part C) of these patients.

Dosing extension to 6 consecutive doses once every 4 weeks

Patients initially receive 4 consecutive doses once every 4 weeks (week 0, 4, 8, 12). Patients will receive 1 or 2 additional doses under the following conditions:

- no treatment related safety issues (for periorbital swelling* only if >grade 2) resulting in dosing delay during the first 4 doses the tumor has not been completely eliminated after the 3rd dose [determined by MRI at week 12]
- the tumor did respond to treatment (Part B: >50 % tumor volume reduction) after the 3rd dose [determined by MRI at week 12] Corporate Confidential Information

In Part C additional criteria apply as following:

- Part C (arms 3 mg/kg or 5 mg/kg): the tumor did respond to treatment (≥45 % tumor volume reduction) after the 3rd dose [determined by MRI at week 12] and MCS110 was tolerated: the patient will receive 3 additional doses of the same as dose level
- Part C (arms 3 mg/kg or 5 mg/kg): the tumor response to treatment is <45 % of tumor volume reduction after the 3rd dose [determined by MRI at week 12] and MCS110 was tolerated: the patient will receive doses increased to 10 mg/kg
- Part C (arm 10 mg/kg): the tumor did respond to treatment (≥45 % tumor volume reduction) after the 3rd dose [determined by MRI at week 12] and MCS110 was tolerated: the patient will receive 3 additional doses of 10 mg/kg

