Eligibility criteria and safety assessments will be similar as in Part B. Patients will also be followed up to 2 years every 4 months and they will be offered another treatment course with 10 mg/kg of MCS110 in case of relapse, where relapse is diagnosed at least 6 months after the last MCS110 dose received during the first treatment course.

Efficacy assessments will include tumor volume reduction, Corporate Confidential Information joint specific questionnaires, VAS and time to relapse.

[figure not shown]

Figure 2-1: Study design Part C – adults and adolescents

Conditions of lower dose arm recruitment extension

If a lower dose is identified with at least the same efficacy as 10 mg/kg, defined as tumor volume reduction evaluated by MRI of at least 45%, additional patients may be enrolled in this lower dose group to extend the arm up to approximately 10 patients. Only one dose level, either 3 or 5 mg/kg may be extended and the additional patients will be allocated to the selected dose level in an open label fashion with the same assessment schedule applied, Corporate Confidential Information

The planned enrollment number in Part C is approximately 15 patients. If a lower dose is identified to be, at least, as efficacious as 10 mg/kg, additional patients may be enrolled in open label to extend the efficacious 3 mg/kg or 5 mg/kg arm to approximately 10 patients.

3 First interpretable results (FIR)

First interpretable results (FIR) will be provided for this trial for each interim analysis and final analysis.

Corporate Confidential Information

Corporate Confidential Information

5 Statistical methods: Analysis sets

Analysis sets will be defined the same for parts A,B and C.

For subjects for which the actual treatment received does not match the randomized treatment the treatment actually received will be used for the analysis.

All patients that received the study drug dose and with no protocol deviations with relevant impact on safety will be included in the safety analysis set.

All patients with at least one available valid (i.e. not flagged for exclusion) PK concentration measurement, who received the study drug and experienced no protocol deviations with relevant impact on PK data will be included in the PK analysis set.

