Additional time-profiles will be provided graphically for circulating monocytes, Creatine Kinase and ALT, AST (liver enzymes). This will be presented for Part A*, Part B* and Part C.

Special clinical laboratory evaluations

All laboratory data will be listed by treatment, patient, and visit/time and if ranges are available abnormalities will be flagged. Summary statistics will be provided by treatment and visit/time.

Adverse events

All information obtained on adverse events will be displayed by treatment and patient. The number and percentage of subjects with adverse events will be tabulated by body system and preferred term with a breakdown by treatment. An adverse event starting in one period and continuing into the next period is counted only in the onset period. A subject with multiple adverse events within a body system [within a treatment period] is only counted once towards the total of this body system.

Frequency counts will be produced for adverse events by maximum severity and the same table produced for adverse events that are related to study drug. An overall summary of the number of adverse events categorised by serious, related, leading to discontinuation and death. Summary statistics will be produced for the duration of adverse events by preferred term.

Additional listing of adverse events of special interest will also be provided. Adverse Events of special interest will be identified by medical review of the preferred terms occurring in the data in addition to periorbital edema already identified.

In Part C all summary tables will also be provided by age group (<18 years and ≥18 years).

Concomitant medications / Significant non-drug therapies

All concomitant therapies will be listed by treatment group and patient.

10 Reference list

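### Read most directly, the SAP's Part C grouping leaves only non-escalated patients in the 3 and 5 mg/kg adverse event columns and mixes low-dose events with later 10 mg/kg events in the escalated groups

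*SAP*

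**What the plan says.** - **Grouping.** SAP 7.1, Part C, defines arms 1 to 3 as 3, 5 and 10 mg/kg. Patients in arms 1 and 2 who move to 10 mg/kg after three doses become groups 4 and 5: "they will be treated as a separate group throughout the study". The scope is wide: "This approach will be applied for all analyses of Part C where the treatment group is used".
- **Adverse event tables.** SAP 8 has events "tabulated by body system and preferred term with a breakdown by treatment". It adds: "An adverse event starting in one period and continuing into the next period is counted only in the onset period". No Part C column rule appears in that section.
- **Who escalates.** Protocol 3.2.2 sets the condition as "If the drug is well tolerated and the tumor volume reduction is <45"% at the week-12 MRI. Protocol 5.5.5.2 repeats the tolerability requirement: "MCS110 was tolerated: the patient will receive doses increased to 10 mg/kg". Protocol 5.5.9 requires withdrawal after a drug-related SAE or a severe hypersensitivity reaction.
- **Periods.** The only Part C treatment period named is in Protocol 5.4: "28 weeks double-blind treatment period study part will be followed by an open label part". It covers the doses before and after week 12.
- **Part B\*.** For the pooled multiple-dose data, SAP 7.1 keeps escalated patients in their original group for the first three doses and moves them to a separate group only afterwards.
- **Re-dosing.** SAP 2.4 says of Part C patients: "they will be offered another treatment course with 10 mg/kg of MCS110 in case of relapse". Protocol 5.5.5.2 replaces this with a lower dose once an equally effective one is identified.

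**The concern.** Protocol 3.2.3.2 gives the aim of Part C as finding a dose that matches 10 mg/kg on efficacy with possibly fewer side effects, and safety is a primary objective (Protocol 2.7). The cleanest evidence on side effects is weeks 0-12, when every randomised patient is on the assigned dose.

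If the SAP 7.1 rule governs the adverse event tables, that comparison is not tabulated. Tolerant non-responders leave the 3 and 5 mg/kg columns and take their weeks 0-12 events with them. Patients who tolerate the low dose badly cannot escalate and stay. The 10 mg/kg column loses nobody. Membership of the low-dose columns then depends partly on the outcome those columns are meant to report.

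**Working it through.** The plan gives no figure for this point beyond the arm sizes, so the check is a reading of the rules followed by an illustration.

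**1. Arm sizes.** Protocol 5.2.3 has about 15 patients at 2:2:1. 15 × 2/5 = 6, 15 × 2/5 = 6 and 15 × 1/5 = 3, which agrees with Table 5-1 (about 6, 6 and 3).

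**2. Which rule reaches the tables.** The visible SAP has two rules for escalated patients. The Part B\* rule would preserve weeks 0-12 by starting dose, but SAP 8 uses Part B\* only for the monocyte, CK, ALT and AST profiles. The Part C rule runs for the whole study and covers all Part C analyses by treatment group. The onset-period sentence would separate the doses only if a period ended at week 12, and SAP 8 defines no such boundary.

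**3. Events that block escalation (assumed counts).** Take an arm of 6 in which *k* patients do not tolerate the dose by week 12 and *e* of the other 6 − *k* escalate.

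- Rate by randomised arm: *k*/6
- Rate in the low-dose column: *k*/(6 − *e*)
- Ratio: 6/(6 − *e*)
- Weeks 0-12 rate among the escalated: 0/*e*

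| *k* | By arm | *e* = 2 | *e* = 3 | *e* = 4 |
|---|---|---|---|---|
| 1 | 1/6 = 17% | 1/4 = 25% | 1/3 = 33% | 1/2 = 50% |
| 2 | 2/6 = 33% | 2/4 = 50% | 2/3 = 67% | 2/2 = 100% |
| Ratio | 1 | 1.5 | 2 | 3 |

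The column rate is never below the rate by arm, so this distortion works against the low dose.

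**4. Mild events that do not block escalation (assumed count).** Suppose 3 of 6 patients have the event in weeks 0-12, which is 50% by arm. The low-dose column can show from max(0, 3 − *e*) to min(3, 6 − *e*) of 6 − *e* patients:

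- *e* = 2: 1 to 3 of 4
- *e* = 3: 0 to 3 of 3
- *e* = 4: 0 to 2 of 2

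The column can fall on either side of 50%, so the direction is not fixed. If escalation is unrelated to the event, the expected rate is unchanged, but the denominator shrinks and the escalated patients' events still leave the column.

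**5. What adding groups recovers.** Groups 1 + 4 and 2 + 5 restore the randomised arms and give whole-study counts of patients with an event. They do not restore weeks 0-12. Suppose group 4 has one patient with onset in week 6 on 3 mg/kg and another with onset in week 18 on 10 mg/kg, and group 1 has none. The sum is 2/6, while the weeks 0-12 count at the randomised dose is 1/6.

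**6. Whether blocking events occur.** The protocol's summary of this study in Section 1 reports four drug-related SAEs in Part C. Protocol 3.5.2 reports five infusion reactions in Part C, two of them SAEs. Doses are not shown, so these show that such events occur and do not give their frequency by dose.

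**The case against.** The strongest objection is that the rule may not reach adverse events. It sits in the tumour-volume section and applies where treatment group is used. SAP 8 breaks adverse events down by treatment, yet lists concomitant therapies by treatment group. The onset-period sentence, with the protocol glossary's definition of a period as a minor subdivision such as titration, could mean attribution by dose at onset. Protocol 9.4.2 also sets a new baseline just before the first 10 mg/kg dose and says this may extend to the other Section 9 analyses, which include safety. This stands as a second possible reading but does not settle the matter. SAP 8 does not explain a difference between the two terms, the Protocol 9.4.2 extension is optional, and SAP 7.1 declines re-baselining for escalated patients in Part B\*.

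It is also fair that no event is lost. The escalated groups and the patient listings keep every event, and with so few patients weeks 0-12 can be rebuilt by hand. Parts of the SAP are redacted and the table shells are not public, so a suitable table may already exist.

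Three stronger readings are tempting, and the documents support none of them:

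- **That side effects are not compared by randomised dose at all.** Adding the groups gives whole-study counts by arm. What is missing is the weeks 0-12 comparison.
- **That the grouping flatters the low dose.** For events that block escalation it does the opposite, and for mild events the direction is unknown.
- **That the ratios of 1.5 to 3 estimate the bias.** They follow from assumed counts and apply only to blocking events. Protocol 3.5.1 describes periorbital swelling as mild in all patients and rash as generally mild.

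**Conclusion.** On the most direct reading of SAP 7.1 with SAP 8, the Part C low-dose adverse event columns are selected after randomisation on week-12 response and tolerability, and groups 4 and 5 combine two dose levels. The SAP states a better rule for Part B\* but does not apply it to adverse events. The text should be changed, though this is a gap in specification and not proof that the final tables will mislead.

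The size is unknown. The illustration assumes an arm of 6, one or two intolerant patients and two to four escalations. It also takes intolerance as barring escalation outright, although the protocol gives no numerical threshold for tolerability. Confidence is medium because of the alternative reading and the redactions.

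A separate, minor point concerns Protocol 3.5.5, which says periorbital oedema is not expected at the lower doses. Protocol 3.5.1 reports periorbital swelling in 15 of 18 Part C patients (83%). If 3 of the 18 started on 10 mg/kg, at least 15 − 3 = 12 of 15 lower-dose starters were affected; if 4 did, at least 11 of 14. A reader might infer that the statement is disproved. It is not, because dose at onset is not shown and some cases may have followed escalation. It is unsupported as written.

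**What to change.** In SAP 8:

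1. Add one descriptive Part C adverse event table, at least for periorbital oedema and rash, from first dose until just before the fourth dose (week 12 if no fourth dose is given). Keep every randomised patient in the randomised arm, put open-label extension patients on a separate line, and state that the table is exempt from the SAP 7.1 grouping.
2. State that later events are attributed to the dose being received at onset. Include events in a re-dosing course, whether at 10 mg/kg or at the lower dose that Protocol 5.5.5.2 allows.

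If the table shells already do this, a clarifying sentence is enough.

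Separately, in Protocol 3.5.5, stop the statement about lower doses from covering periorbital oedema and refer to the counts in 3.5.1.

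The cost is one table, one attribution sentence and one edited protocol sentence. With 3 to 6 patients per arm the table will be imprecise. The exact 95% upper limit is 1 − 0.025^(1/6) = 46% for 0/6 and 1 − 0.025^(1/3) = 71% for 0/3. It should be labelled descriptive and not used for a formal comparison.
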